6.4 Non-clinical summary

GS-248 inhibits mPGES-1 enzyme with a half maximal inhibitory concentration (IC₅₀) of 2 nM, while having no effect on COX-1 or COX-2 when tested up to 100 μM. In a human whole blood assay (WBA), GS-248 inhibited PGE₂ synthesis with an IC₅₀ of 0.4 nM. Efficacious enzyme inhibition *in vivo* has been demonstrated in a Thermal Hyperalgesia model in the guinea-pig in which GS-248 reversed the lipopolysaccharide (LPS)-induced hyperalgesia in a dose dependent manner with maximal effect at 30 mg/kg p.o., 3 h post-dose.

The core battery safety pharmacology studies performed showed that GS-248 had no central nervous system (CNS), respiratory or cardiovascular effects after single or repeated administration at doses of up to 1000 mg/kg in rats or 80 mg/kg in dogs.

GS-248 in rat demonstrated an intermediate clearance compound with a large volume of distribution, with an oral bioavailability of 37% and a terminal half-life (T_{1/2}) of 2.5 h in the fasted state. The overall steady state toxicokinetic data in the rat and dog showed that the exposure increased less than dose proportionally, except for female dogs between the low and intermediate doses on test day 1 and between the intermediate and high doses on test day 18/28, where the increase was dose proportional. The mean exposure (male and female dogs) at the no observed adverse effect level (NOAEL) were 2500 nmol/L for maximum plasma

concentration (C_{max}) and 23000 nmol*h/L for $AUC_{(0-last)}$. No accumulation was observed in the rat, whereas an accumulation was observed over the number of treatment days in the dog.

GS-248 showed a high plasma protein binding in all investigated species, with human serum albumin as the major determined protein in human plasma. Radiolabelled GS-248 was extensively distributed with the highest concentrations found in the liver, adrenals, brown fat, kidneys, salivary glands, and pancreas. After reaching the maximum, radioactivity in tissues and organs depleted rapidly within the first 8 h.

An *in vitro* metabolism species comparison showed no major difference in metabolic pathways between rat, dog, cynomolgus and human hepatocytes. GS-248 has been shown to be a potent *in vitro* inhibitor for CYP 2C8, 2C9 and 2C19.

The major part of GS-248 in rats was eliminated in faeces via the bile whereas urinary excretion was negligible. Overall, the elimination was fast and almost complete after 48 h.

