Testicular degeneration was noted histopathologically in the 3 male dogs at the highest dose level in the 28-day study that were necropsied pre-terminally on Day 21. These changes were interpreted as most probably being secondary effects as a result of the poor physiological condition of these animals, and therefore not directly related to GS-248 treatment. Furthermore, as no such changes were noted at the NOAEL (the intermediate dose level) in this study, there will be sufficient safety margins to such effects in the present study.

The phototoxicity of GS-248 has not been investigated, but based on the MEC value obtained from absorbance studies and the weak and comparatively short-lived potential binding of radioactivity to melanin-containing tissues of the ocular bulb, a phototoxic potential cannot be excluded. Thus sun protection, as defined in Section 9.5.2, should be used during the study.

The selection of starting-dose and dose-escalation steps represents a careful approach to administer GS-248 for the first time in humans (see Section 8.3). Sentinel dosing will apply for the first 2 subjects in each SAD cohort.

SSc patients participating in the study may experience some symptom relief. The risks for SSc patients are considered to be comparable to those identified for the healthy volunteers participating in Part I and Part II of the study with the exception that patients may experience

discomfort following withdrawal of e.g. proton pump inhibitors (PPIs) and other medications (see below).

In Part I, II and III, use of antacids, PPIs or any medication that changes gastric pH is disallowed from 14 days prior to IMP administration and during the study since GS-248 is a low solubility compound with pH dependent solubility. A high pH may decrease exposure.

Use of NSAIDs, coxibs and aspirin is prohibited from 14 days prior to IMP administration and during the study to avoid interference with the GS-248 signal transduction pathway and evaluation of study results.

The iSRC will monitor emerging safety and PK data over the course of the study and must give a favourable recommendation prior to any dose escalation, see Section 8.3.7 and Section 8.3.8 for stopping criteria for dose escalation and for further information about the iSRC.

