8.3.3 *Selection of starting dose and dose escalation in the MAD part*

The starting dose in the MAD part of the study will be selected with the aim to achieve an exposure similar to that observed in the third cohort in the SAD part, and is tentatively set to 25 mg. The doses in the second and third MAD cohorts will be selected to achieve an

escalation of exposure of approximately 3 times of what was observed in the previous cohort. The dose in the fourth (and potential fifth) MAD cohort will be selected to achieve an exposure twice of what was observed in the previous cohort. Tentative doses are displayed in Table 8.3-3.

Table 8.3-3 Tentative dose escalation schedule MAD

| Cohort: | 1 | 2 | 3 | 4 |
|--|-----------------|----------|----------|------------------|
| Maximum exposure escalation steps | | 3x | 3x | 2x |
| Tentative doses (mg) | 25 ¹ | 75 | 225 | 450 ² |

1. Aimed to achieve an exposure similar to that in the third cohort of the SAD part.
2. Projected exposure not exceeding what was achieved by the study maximum dose given in the SAD part in terms of AUC_{0-∞}.

If the systemic exposure following any of the first 3 cohorts is appreciably larger than projected, escalation steps will be decreased. In case of limiting safety or tolerability, de-escalation may be performed. The decision on dose selection will be made by the iSRC, which will have access to all safety, tolerability and PK data as outlined in Section 8.3.8.

PK information from the SAD part will give the terminal T_{1/2} of the drug, which in turn, will indicate potential accumulation of GS-248. The dose, or dosing interval, will be adjusted accordingly if such is identified. If safety and tolerability allows, the aim is to, in the last MAD cohort, reach a maximum exposure in terms of AUC_{0-tau} not exceeding what was achieved by the study maximum dose given in the SAD part in terms of AUC_{0-∞}.

8.3.4 *Maximum exposure and dose*

The maximum dose to be given is 800 mg/day. The maximum exposure in the study may not exceed 2500 nmol/L or 23 000 h*nmol/L in terms of C_{max} and AUC, respectively, based on C_{max} and AUC₀₋₂₄ at the dog NOAEL (males and females combined).

8.3.5 *From single to multiple dosing*

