| If 2 subjects on active treatment have severe, non-serious AEs assessed at least possibly related to the IMP administration (independent of within or not within the same System organ class [SOC]) | 
 1. Stop dosing of subjects with severe, non-serious potential ADRs. 2. Unblinding of the subjects with potential ADRs. Only voting members of the iSRC will be unblinded. 3. Evaluation by iSRC. The iSRC makes recommendation to Sponsor. 4. Sponsor decides how to proceed: Both subjects meet stop criterion: stop further dosing at this dose level for all subjects. Sponsor decides if the study will be terminated or if dosing should commence at a lower dose level or at an intermediate dose level. |
| If 1 subject has an $AUC_{0-\infty}$ (single dose) or $AUC_{0-\tau}$ (repeated dose) higher than 23 000 h*nmol/L (corresponding to the NOAEL in male and female dogs) ¹ | 
 1. Evaluation by iSRC. The iSRC makes recommendation to Sponsor. 2. Sponsor decides if the study will be terminated or if dosing in the next cohort should commence at a lower dose level or at an intermediate dose level. |
| If 1 subject has a C_{max} higher than 2500 nmol/L (corresponding to the NOAEL in male and female dogs) ¹ | 
 1. Evaluation by iSRC. The iSRC makes recommendation to Sponsor 2. Sponsor decides if dosing in the next cohort should commence at a lower dose level or at an intermediate dose level. |
| Final dosing stop and termination of study | |
| If 2 subjects on active treatment in different cohorts have SAEs assessed as at least possibly related to IMP administration | 
 1. Stop dosing of subjects with potential SADR. Withdrawal of subjects. 2. Unblinding of subjects with potential SADR. Only voting members of the iSRC will be unblinded. 3. Evaluation by iSRC. The iSRC makes recommendation to Sponsor. 4. Subjects meet stop criterion: Termination of study. |

1. When reviewing emerging data in relation to this criterion, the maximum exposure observed in individual subjects within a cohort rather than the mean exposure should be taken into account

8.3.8 *Internal safety review committee*

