The duration of the residential periods in each part may be amended following review of data from earlier cohorts. The predicted $T_{1/2}$ of GS-248 is between 2 and 13 h, based on allometric scaling of preclinical data. A significantly shorter $T_{1/2}$ than expected, as determined following analysis of PK data in the study, may warrant a shortening of the residential period provided that no safety issues are indicated. Conversely, if indicated by safety and or PK data, the duration of the residential periods may be prolonged. Should the duration of any residential period change, subsequent changes to the timing of safety and PK assessments will be done as necessary. A significantly shorter $T_{1/2}$ than expected may also require a change in the dosing interval, i.e. twice daily GS-248 dosing rather than once daily dosing might be required in order to reach sufficient exposure. Such changes to the CSP (Part I, II or IV with healthy volunteers) will be documented in non-substantial amendments. A substantial amendment will be submitted to both the CA and the IEC prior to start of Part III (SSc patients) of the study, see Section 8.3.6.

The treatment code may be broken by the iSRC during the assessment process (partial unblinding) in accordance with stopping criteria described in Table 8.3-4. The medical staff and the subjects will still be blinded for the treatments (active drug or placebo) to be administered in the subsequent dose groups/cohorts in order to minimise bias. If unblinding was considered necessary, the iSRC meeting will consist of a closed part and an open part.

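### Table 8.3-4 contains no interim hold on dosing when one subject exceeds the Cmax or AUC cap; the gap matters only if PK results return while Part II dosing is under way

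*Protocol*

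**What the plan says.** Protocol 8.3.4 sets the limit: "The maximum exposure in the study may not exceed 2500 nmol/L or 23 000 h*nmol/L", for Cmax and AUC respectively, taken from the dog NOAEL. Footnote 1 to Table 8.3-4 (section 8.3.7) says that in applying it "the maximum exposure observed in individual subjects within a cohort rather than the mean exposure should be taken into account".

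The table's two exposure rows are each triggered by one subject. Both start with an evaluation and recommendation by the iSRC. In the Cmax row, the sponsor's step is then: "Sponsor decides if dosing in the next cohort should commence at a lower dose level or at an intermediate dose level". The AUC row is the same, except that the sponsor may also terminate the study. The AUC row names the repeated-dose AUC over the dosing interval, so exceedances in Part II were foreseen.

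Part II gives one dose a day for 10 days (8.1.2). The required iSRC review of a Part II cohort uses data up to 24 h after the last dose and precedes the next cohort (8.1.2, 8.3.8). Section 6.7 also states: "The iSRC will monitor emerging safety and PK data over the course of the study". No turnaround time for PK results is given.

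**The concern.** The cap is worded as a limit that must not be passed, but the table that lists the actions has no step for the person who has passed it. The rows for one related SAE and for two severe related AEs both open with an instruction to stop dosing the subjects affected. The exposure rows have no such instruction, and no pause on starting further subjects at that dose level. Section 9.7 has QTc and liver withdrawal criteria and general criteria that rest on judgement, but none based on exposure.

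In Part I this hardly matters for the affected subject, who has only one dose. In Part II, a subject over a cap on Day 1 has up to 9 doses to come. Section 6.4 identifies dog liver and biliary toxicity as the finding that limits human exposure, and 6.7 says that healthy volunteers gain no medical benefit beyond health examinations. A known breach should therefore not depend on how soon a committee can meet before the next morning's dose.

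**Working it through.** **1. Is there a mandatory subject-level stop on exposure?**

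| Place in the protocol | Trigger | Mandatory stop for the subject? |
|---|---|---|
| Table 8.3-4, SAE and severe-AE rows | Related SAE; two severe related AEs | Yes, step 1 |
| Table 8.3-4, AUC and Cmax rows | One subject over a cap | No: iSRC evaluation, then sponsor decision |
| 8.3.4 | Either cap | A limit, with no action attached |
| 8.3.7, ad hoc iSRC meetings | Trends or safety signals | No, discretionary |
| 8.3.8, no repeat of a dose level that met a stopping rule | Any stopping rule | No, concerns the next dose level |
| 9.7.1 | Judgement criteria, including significant AEs | No, discretionary |
| 9.7.2, 9.7.3 | QTc, liver chemistry | Yes, but not on exposure |

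**2. Doses at stake.** If the Day 1 result arrives k days after Day 1, the doses that can still be withheld number 10 − (1 + k) = 9 − k: 8, 6, 4, 2 and 0 for k = 1, 3, 5, 7 and 9. The documents do not give k.

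**3. Would a Day 1 exceedance fade?** The predicted half-life "of GS-248 is between 2 and 13 h, based on allometric scaling of preclinical data" (8.3.8). Once-daily accumulation is R = 1/(1 − 2^(−24/t)), which is 1.00 at t = 2 h and 1.39 at t = 13 h. Exposure would be expected to hold or rise. The animal evidence is mixed: "an accumulation was observed over the number of treatment days in the dog", but the same sentence of 6.4 reports none in the rat.

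**4. Exposure at the planned top dose.** Table 8.3-1 predicts, at 1 mg, a Cmax of 4.6–5.6 nmol/L and an AUC of 19–31. Its margins reproduce: 2500/5.6 = 446 (printed 450) and 23 000/31 = 742 (printed 740). The AUC predictions in Table 8.3-2 are close to proportional: 8700/19 = 458 and 14 000/31 = 452 for a 450-fold dose. No Cmax above 1 mg is printed.
- Proportional Cmax at 450 mg: 450 × 4.6 = 2070; 450 × 5.6 = 2520.
- Dog Cmax, 5 to 20 mg/kg: 2500/1400 = 1.79 for a 4-fold dose, exponent ln 1.786/ln 4 = 0.418. If that held from 1 mg upward, Cmax at 450 mg would be 4.6 × 450^0.418 = 59 to 5.6 × 450^0.418 = 72 nmol/L, far below the cap.

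**5. Chance of a first breach in Part II at 450 mg.** The documents give no between-subject CV, so 20–50% is assumed. Further assumptions: lognormal exposure, independent subjects, 6 on active drug per cohort, the same distribution in Parts I and II, and a Part I breach blocking that dose. With s = √ln(1 + CV²), p = 1 − Φ(ln(cap/median)/s) and q = (1 − p)^6, the chance is q(1 − q), which cannot exceed 0.25.

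Example, Cmax median 2070 and CV 20%: s = 0.198, p = 0.170, q = 0.326, q(1 − q) = 0.220.

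| 450 mg | CV 20% | 30% | 40% | 50% |
|---|---|---|---|---|
| Cmax, median 2070 | 0.220 | 0.137 | 0.095 | 0.073 |
| Cmax, median 2520 | 0.013 | 0.014 | 0.014 | 0.014 |
| AUC, median 8700 | 0.000 | 0.003 | 0.033 | 0.100 |
| AUC, median 14 000 | 0.035 | 0.184 | 0.249 | 0.237 |

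The AUC rows strictly describe a steady-state dosing interval. On Day 1, the AUC to 24 h would be 72–100% of that for half-lives of 13 to 2 h (1 − 2^(−24/t)).

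**6. The doses reported.** SAP 3.4 gives Part II doses of 20, 60 and 180 mg. Proportional scaling to 180 mg gives a Cmax of 828–1008 nmol/L (33–40% of the cap) and an AUC of 3420–5580 (15–24%). The chance that at least 1 of 6 exceeds is 1 − q:

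| 180 mg | CV 20% | 30% | 40% | 50% |
|---|---|---|---|---|
| Cmax, median 828 | 0.000 | 0.001 | 0.012 | 0.057 |
| Cmax, median 1008 | 0.000 | 0.006 | 0.054 | 0.153 |
| AUC, median 3420 | 0.000 | 0.000 | 0.000 | 0.000 |
| AUC, median 5580 | 0.000 | 0.000 | 0.001 | 0.008 |

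**7. Pausing new starts.** At most 4 of the 8 Part II subjects start on one day (8.1.2), so at least 8 − 4 = 4 start later. Two of the 8 receive placebo, so as few as 4 − 2 = 2 later starters may be on active drug.

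**The case against.** A reader might infer that the table permits continued dosing of a subject known to be over the cap. It does not: it is silent on the matter, 8.3.4 points the other way, and the iSRC must evaluate. The iSRC may recommend that dosing stop, and if its two voting members disagree on the next dose level, the more conservative course is recommended (8.3.8). What is missing is an automatic hold while that happens.

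The rows also sit under stopping criteria for dose escalation, and an action on the next cohort suits a review held after the last dose. Adverse events are seen as they occur; PK samples are stored frozen until analysed (12.3), and nothing schedules their analysis within a cohort. The timing and content of iSRC review are left to a charter that is not among the documents and may contain a rule. This stands, and it makes the concern conditional. The stated monitoring of emerging PK data leaves within-cohort results possible without showing that they occur.

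The toxicity behind the cap has its own mandatory stop: clinical chemistry is taken on Days 2, 3, 6 and 9 during Part II dosing, and 9.7.3 stops treatment at liver thresholds. That reduces the risk, but it acts on injury already detectable, not on the exposure breach.

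The printed AUC of up to 25 000 in Table 8.3-2 (25 000/23 000 = 1.09) might be read as a predicted breach in Part II. It belongs to an optional single-dose cohort, where withholding further doses has no meaning. Section 8.3.3 says "the aim is to, in the last MAD cohort, reach a maximum exposure in terms of" AUC over the dosing interval no higher than that of the top SAD dose, and 8.3.5 keeps predicted MAD exposure within that of evaluated SAD cohorts. Animal data "showed that the exposure increased less than dose proportionally, except for female dogs" under some conditions, escalation is PK-driven, and 8.3.3 adjusts dose or interval for accumulation. All of this lowers the chance of a breach in Part II.

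**Conclusion.** The gap in the text is real and should be closed, but its effect is conditional. Following either exposure row as written leaves an over-cap subject due for the next daily dose, with no hold until the iSRC acts. This has consequences only if a result returns during Part II dosing, and only if a breach occurs.

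On the plan as designed (450 mg), a first breach in Part II has a chance of about 1–22% for Cmax and 0–25% for AUC. These figures rest on proportional scaling and an assumed CV of 20–50%; with the dog's less-than-proportional exponent, the Cmax cap would not be approached. At the reported maximum of 180 mg, the chance that at least 1 of 6 exceeds is under 1% for AUC and 0–15% for Cmax, and under 1% for Cmax at a CV of 30% or less. The practical consequence at the doses given was therefore probably small. The documents do not support inferring that any subject was overdosed or that the plan allows it.

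**What to change.** Insert as the first step of both the AUC row and the Cmax row of Table 8.3-4:

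> *If the result is available while dosing at this level is ongoing, withhold further dosing of the subject concerned and do not start further subjects at this level until the iSRC has evaluated; other subjects already being dosed continue unless the iSRC recommends otherwise.*

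Leave the limit in 8.3.4 as it is; at most, add a cross-reference to the table for the action in Parts I and II.

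No new samples and no change in bioanalytical timing are needed. The costs are these. Dosing staff may infer active treatment from a withheld dose, whereas the adverse-event rows confine unblinding to the iSRC's voting members. The withheld subject may lose Day 10 PK/PD data. The step has no effect in Part II if samples are analysed only after Day 10. The pause on new starts could spare up to 4 later starters, with as few as 2 on active drug, and only if the result arrives before they start.

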9 STUDY POPULATION

Prospective approval of protocol deviations to eligibility criteria, also known as protocol waivers or exemptions, is not permitted.

9.1 Recruitment

For Part I, II and IV, the subjects will be recruited from CTC's database of healthy volunteers and from advertising in media (including social media).

Subjects may participate in more than one part of the study provided that the eligibility criteria for each part are met.

The patients for Part III will be identified by referring rheumatologists.

9.2 Screening and enrolment log

Investigators must keep a record of all screened subjects even if they were not subsequently included in the study. This information is necessary to verify that subjects were selected without bias. The reason for screening failure should be stated for all subjects screened but not included. The reason for withdrawal should be stated for all subjects included but not completed.

A screening number will be allocated to each subject in connection to the informed consent process at the Screening visit. The screening number is generated automatically in the electronic case report Form (eCRF). The screening number will allow identification of subjects irrespective of their possible eligibility for the study.

Subjects included and randomised will be assigned a randomisation number (1101, 1102 etc. in the Part I, cohort 1; 2101, 2102 etc. in the Part II, cohort 1 and so on). The first digit will correspond to the study part, the second digit will correspond to the cohort and the 3rd and 4th digits correspond to the subject number.

If a subject/patient cannot receive the planned dose of IMP within 27 days/41 days after screening (*i.e.*, the time interval between signing informed consent until dose administration) the subject should be re-screened before proceeding in the study.

9.3 Number of subjects/patients

Part I (SAD): 48 subjects will be randomised and dosed (6 cohorts, each of 8 subjects: 6 GS-248, 2 placebo).

Part II (MAD): 32 subjects will be randomised and dosed (4 cohorts, each of 8 subjects: 6 GS-248, 2 placebo).

Part III (SSc patients): 10 SSc patients will be randomised and dosed (1 cohort with 10 subjects: 8 GS-248, 2 placebo).

Part IV (celecoxib): 8 subjects will be randomised and dosed (1 cohort with 8 subjects receiving celecoxib).

If indicated by emerging data and recommended by the iSRC, 2 additional cohorts (8+8 subjects) may be added to Part I, 1 cohort (8 subjects) may be added to Part II and 1 cohort (10 patients) may be added to Part III. In such cases, and to account for potential drop-outs, additional subjects might be included in the study.

For replacements of subjects who discontinue from the study, see Section 9.7.5.

9.4 Eligibility criteria

9.4.1 *Inclusion criteria Part I, II and IV: SAD, MAD and celecoxib in healthy volunteers*

For inclusion in Part I, II and IV of the study, subjects must fulfil the following criteria:

1. Willing and able to give written informed consent for participation in the study.
2. Male and female healthy subjects aged 18-70 years inclusive (Part I [SAD]) and 40-75 years inclusive (Part II [MAD] and Part IV [celecoxib])
3. Women of child bearing potential (WOCBP) must practice abstinence (only allowed when this is the preferred and usual lifestyle of the subject) or must agree to use a highly effective method of contraception with a failure rate of < 1% to prevent pregnancy (combined [oestrogen and progestogen containing] hormonal contraception associated with inhibition of ovulation [oral, intravaginal, transdermal], progestogen-only hormonal contraception associated with inhibition of ovulation [oral, injectable, implantable], intrauterine device [IUD] or intrauterine hormone-releasing system [IUS]) from at least 4 weeks prior to dose to 4 weeks after last dose. Their male partner must agree to use a condom during the same time frame.

Women of non-childbearing potential are defined as pre-menopausal females who are sterilised (tubal ligation or permanent bilateral occlusion of fallopian tubes); or post-menopausal defined as 12 months of amenorrhoea (in questionable cases a blood sample with simultaneous detection of follicle stimulating hormone [FSH] 25-140 IE/L and oestradiol <183 pmol/l is confirmatory).

Male subjects must be willing to use condom or be vasectomised or practice sexual abstinence to prevent pregnancy and drug exposure of a partner and refrain from donating sperm from the date of dosing until 3 months after dosing with the IMP. Their female partner of child-bearing potential must use contraceptive methods with a failure rate of < 1% to prevent pregnancy (see above).

4. Body mass index (BMI) ≥ 19 and ≤ 30 kg/m².
5. Subjects must be in good health as determined by medical history, physical examination, vital signs, 12-lead ECG and clinical laboratory assessments at the time of screening, as judged by the Investigator.

9.4.2 *Exclusion criteria Part I, II and IV: SAD, MAD and celecoxib in healthy volunteers*

Subjects must not enter the study if any of the following exclusion criteria are fulfilled:

1. Known allergy to any components of the GS-248 formulation.
2. Females who are breast feeding or plan to be pregnant.

3. Positive serum or urine pregnancy test (minimum sensitivity 25 IU/L or equivalent units of human chorionic gonadotropin [HCG]) at screening and within 24 h prior to the first administration of IMP.
4. Use of corticosteroids (inhaled and systemic), NSAIDs (including e.g. coxibs and aspirin), antacids, PPIs or any medication that changes gastric pH within 2 weeks prior to the (first) administration of IMP.
5. Regular use of any prescribed or non-prescribed medication including analgesics, herbal remedies, vitamins and minerals within 2 weeks prior to the (first) administration of IMP, except hormonal contraception and occasional intake of paracetamol (maximum 2000 mg/day; and not exceeding 3000 mg/week) and nasal decongestants without cortisone, antihistamine or anticholinergics for a maximum of 10 days, at the discretion of the Investigator.
6. Inherited or acquired disorders of platelet function, bleeding or coagulation.
7. Presence of any clinically relevant acute or chronic disease that could interfere with the subject's safety during the clinical study or expose the subject to undue risk.
8. After 10 minutes supine rest at the time of screening, any vital signs values outside the following ranges:
 - Systolic blood pressure <90 or >140 mmHg, or
 - Diastolic blood pressure <50 or >90 mmHg, or
 - Pulse <40 or >90 bpm
9. Any positive result on screening for serum hepatitis B surface antigen (HBsAg), hepatitis C virus antibodies (HCVAb) or human immunodeficiency virus (HIV) 1 and/or 2 antibodies at screening.
10. Presence or history of drug and/or alcohol abuse and/or excessive intake of alcohol and/or history, or current use, of anabolic steroids, as judged by the Investigator.
11. Any positive result for drug abuse and/or alcohol at screening or on admission to the unit prior to administration of the IMP.
12. Participation in another clinical study with an experimental drug within 3 months before the administration of IMP.
13. Consumption of grapefruit or grapefruit juice within 14 days of study drug administration.
14. Any clinically significant illness, medical/surgical procedure or trauma within 4 weeks of the first administration of IMP.
15. Malignancy within the past 5 years with the exception of in situ removal of basal cell carcinoma or resected benign colonic polyps.
16. Any planned major surgery within the duration of the study.
17. Prolonged QTcF (>450 ms), cardiac arrhythmias or any clinically significant abnormalities in the resting ECG at the time of screening, as judged by the Investigator.

18. Current smokers or users of nicotine products. Irregular use of nicotine (e.g. smoking, snuffing, chewing tobacco) less than 3 times per week is allowed before screening visit.
19. Regular excessive caffeine consumption defined by a daily intake of >5 cups of caffeine containing beverages.
20. Intake of xanthine and/or taurine containing energy drinks within 2 days prior to screening.
21. Plasma donation within one month of screening or blood donation (or corresponding blood loss) during the three months prior to screening.
22. Investigator considers the subject unlikely to comply with study procedures, restrictions and requirements.

Part IV, celecoxib only:

History of salicylate hypersensitivity or NSAID hypersensitivity or subjects who have experienced asthma, urticaria or other allergic reactions after taking aspirin or other NSAIDs.

